## **8. Study size**

Expected new entries are of 10 patients per month at the Centre de Soins pour Personnes Agées. The recruitment potential is 50 patients over the duration of the study.

Taking into account possible refusals to participate, patient availability and service organization, we plan to enroll 45 patients.

## **9. Duration**

- Duration of the inclusion period: 5 months
- Participation duration of each participant: 1 hour
- Total duration of the research: 5 months

## **10. Statistical aspects**

The parameters collected will be presented in tables with descriptive statistics for the entire study population and sub-populations (patients with hearing impairment and patients without hearing impairment).

The correlation study between the overall score obtained at the lack of word questionnaire and the score obtained at the hearing questionnaire will be presented in a scatter plot and the Pearson correlation coefficient will be calculated.

The study of the relationship between factors and word deficiency in patients with Alzheimer's disease or related disorders will be carried out by bivariate analysis and then by logistic regression.

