### **1. Justification / context**

In France, Alzheimer's disease accounts for 70 to 80% of the causes of neurocognitive disorders, i.e. 600,000 to 800,000 patients. It is a neurodegenerative pathology that causes evolutionary cognitive dysfunction, mainly affecting memory functions. The inability to name familiar objects (lack of the word) is one of the most commonly noted symptoms at an early stage of the disease.

Presbycusis, or age-related hearing loss, is the most common sensory deficit in the elderly which is manifested socially by a progressive discomfort of verbal communication. Presbycusis remains underdiagnosed and undertreated: 2/3 of the patients are not using hearing aid.

In recent years, a link between neurocognitive disorders and hearing loss has been shown by investigating general cognition. In this study, we are investigating lexical disorders.

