### **2. Objectives**

#### **2.1. Main objective**

To determine the relationship between word loss and presbycusis suspected or proven in patients with Alzheimer's disease or related disorders.

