#### **2.2. Secondary objective**

Study variables associated with word loss in patients with Alzheimer's disease or related disorders.

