### **3. Outcome measures**

#### **3.1. Primary outcome measure**

The lack of word score (BIMM questionnaire) according to the score at the hearing questionnaire.

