#### **3.2. Secondary outcome measure**

Age, gender, socio-cultural level, accommodation, laterality, main diagnosis, hearing aid, speech language therapy according to lack of word score.

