### **4. Outline of the research**

Monocentric study on a series of cases.

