### **5. Eligibility criteria**

#### **5.1. Inclusion criteria**

- > 65 years old
- French mother tongue
- Good vision with or without correction
- Alzheimer's or related disease (15 <Mini-Mental State Examination<25)
- Affiliate or beneficiary of a social security
- Informed consent

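### Section 10 answers the main objective with a crude Pearson coefficient and no confidence interval, and no planned analysis commits to an adjusted hearing-naming estimate

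*Combined protocol and SAP*

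**What the plan says.** The main objective (Section 2.1) is "To determine the relationship between word loss and presbycusis suspected or proven" in patients with Alzheimer's or related disease. The primary outcome (Section 3.1) is "The lack of word score (BIMM questionnaire) according to the score at the hearing questionnaire". Section 10 gives this one inferential summary: the correlation between the two scores "will be presented in a scatter plot and the Pearson correlation coefficient will be calculated". No interval, test, significance level or covariate is attached to it. Section 10 also promises descriptive tables for patients with and without hearing impairment.

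The secondary objective (Section 2.2) is separate and begins "Study variables associated with word loss in patients with". Its measures are in Section 3.2: "Age, gender, socio-cultural level, accommodation, laterality, main diagnosis, hearing aid, speech language therapy according to lack of word score". Section 10 serves it with bivariate analyses followed by a logistic regression of unspecified factors on word deficiency.

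Three other places bear on the point. Section 1 states: "Presbycusis, or age-related hearing loss, is the most common sensory deficit in the elderly". Section 4 describes the design as "Monocentric study on a series of cases". Section 12 says that, if a link is shown, a larger multicentre study must confirm it, and then mentions hearing screening and changes to speech therapy as possibilities.

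**The concern.** The protocol itself ties hearing loss to age. If naming also varies with age or with socio-cultural level, a crude r mixes that shared dependence with any hearing-naming link. Read alone, it cannot tell the two apart. Both variables are on the study's own list, so the information needed to address this is available but not put to that use.

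The missing interval is a second, simpler gap. It needs no assumption about confounding: with 45 patients at most, a bare coefficient does not show how loosely it is estimated.

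What is at stake is the statement that a link has or has not been shown, which Section 12 makes the trigger for the next study.

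**Working it through.** **Inputs from the documents.** Accrual of 10 patients per month and planned enrolment of 45 (Section 8); 5 months of inclusion (Section 9); incomplete patients not replaced (Section 7.3). The plan gives no target correlation, power or precision.

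**The plan's own figure.** 10 × 5 = 50 reproduces the stated recruitment potential. The step from 50 to 45 is a judgement about refusals and organisation with no stated rate, so 45 is a feasibility number and says nothing about precision.

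**Does any planned analysis adjust the hearing-naming estimate?**
- Pearson r: no covariates.
- Tables by hearing group: they can reveal an imbalance in age or socio-cultural level but do not correct for it.
- Logistic regression: it belongs to the secondary objective. Its factors are not listed, Section 3.2 does not include the hearing score, and no cut-off defines word deficiency. Hearing is neither excluded nor named.

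No analysis therefore commits to an adjusted estimate.

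**Precision.** The Fisher interval is tanh(atanh(r) ± 1.96/√(n − 3 − k)), with k covariate terms. For r = 0.30, atanh(r) = 0.3095.
- n = 45, k = 0: 1.96/√42 = 0.3024, giving 0.01 to 0.55.
- r = 0.20, n = 45, k = 0: −0.10 to 0.47.
- r = 0.30 with 40 completers (an assumption; the plan gives no rate): −0.01 to 0.56.

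**Possible confounding.** All correlations here are assumptions, with both scores oriented so that higher means worse. With no direct link and two uncorrelated factors, expected crude r = a₁b₁ + a₂b₂, where a is a factor's correlation with hearing and b its correlation with naming. Age comes first, socio-cultural level second.

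| Scenario | Calculation | Expected crude r |
|---|---|---|
| Mild | 0.2×0.2 + 0.1×0.2 | 0.06 |
| Moderate | 0.3×0.3 + 0.2×0.3 | 0.15 |
| Moderate | 0.4×0.3 + 0.2×0.3 | 0.18 |
| Strong | 0.5×0.4 + 0.3×0.4 | 0.32 |
| No relation to naming | 0.5×0 + 0.3×0 | 0 |

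Adjusting for both factors subtracts exactly these products, so the expected partial correlation is 0, provided no other confounder exists.

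**Cost of adjusting.** The critical value is |r| = t/√(t² + df), with df = n − 2 − k. It serves only as a yardstick, since the plan states no test. At n = 45:
- k = 0 (df 43): 0.294
- k = 2 (df 41): 0.301
- k = 4 (df 39): 0.308

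The 95% interval for r = 0.30 moves from 0.01 to 0.55 (k = 0), to 0.00 to 0.55 (k = 2) and −0.01 to 0.56 (k = 4).

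**The case against.** The best reply is that the plan does what it sets out to do. The objective asks for a relationship, the outcome is one score according to another, and a correlation describes that. The documents support only the hearing-age side of the argument. They are silent on whether age or socio-cultural level affects naming, so every confounding figure above is assumed and the true bias may be nil. The study is a case series, and Section 12 already requires confirmation before anything follows. Participation is a single visit of about an hour, so there is no follow-up attrition to erode the 45.

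Most of this stands, and it limits the weight of the point. It does not meet the missing interval, which needs no confounding assumption. Nor does it explain why an adjustment available from listed variables, at almost no loss of precision, should be left out.

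A reader might go further and infer three things that the documents do not support:
- That no adjusted analysis is planned at all, or that the logistic model excludes hearing. The factors are simply not listed, so the text only fails to commit.
- That the crude r will exaggerate the link. Neither the size nor the direction of any distortion is given.
- That screening would be introduced on the strength of this coefficient. Section 12 puts the confirmatory study first and words screening as a possibility.

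**Conclusion.** The point holds in a limited form. That the interval and a committed adjusted estimate are absent is certain from the text. How much the second omission matters is not. It depends on correlations with naming that the documents do not give, and the range of 0 to 0.32 is illustrative. The precision figures rest only on the Fisher approximation and on having 45 patients with complete data.

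The crude r is a legitimate description and should stay; the defect is that it stands alone. Adjusting for age and socio-cultural level would remove confounding by those two variables only, so it should not be presented as isolating an effect of hearing. Severity is modest: worth correcting before analysis, but not a threat to a study of this kind.

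**What to change.** Replace the correlation sentence in Section 10 with text along these lines:

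> The main objective will be reported with a scatter plot, the crude Pearson r and its 95% confidence interval, and a linear regression of the continuous BIMM overall score on the hearing score, adjusted for age and socio-cultural level (coding fixed before analysis). The adjusted slope and the partial correlation will be given with 95% confidence intervals and the number of patients analysed.

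Add that any statement of a link under Section 12 will rest on the adjusted estimate read beside the crude r, and that residual confounding, for example by disease severity, may remain.

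Give the reasons for the short covariate list. The other Section 3.2 variables (gender, accommodation, laterality, main diagnosis, hearing aid, speech therapy) are left out to keep the model small at 45 patients. Hearing aid and speech therapy are left out also because they may follow from hearing or naming loss.

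A sensitivity model adding MMSE is optional if the value used for eligibility (Section 5.1) is recorded. It is best kept as a sensitivity model because hearing may itself affect a spoken test.

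Naming the hearing score in the existing logistic model would be a smaller edit, but it would still need a cut-off and would split a continuous score.

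The cost is a wording change, with no new patients or visits. The MMSE model might need one extra field in the case report form. The loss of precision is the small one shown above: two terms if socio-cultural level is coded as a number, more if it is coded in categories.

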## **12. Expected benefits**

If this study does show a link between presbycusis and lexical disorders in patients with Alzheimer's disease or related disorders, a new study will be required in a larger, multicentre population to confirm the results.

Prevention and management of patients with Alzheimer's disease or related disorders could be improved. Indeed, systematic screening for hearing disorders could be considered as soon as Alzheimer's or related diseases are suspected. In addition, in these patients, speech and language therapy management may evolve to include two areas: management of language and memory disorders, and management of hearing disorders.

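### Does the primary Pearson correlation need a prespecified interval, test or rank-based replacement?

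*Combined protocol and SAP*

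**What the plan says.** The primary outcome in Section 3.1 is "The lack of word score (BIMM questionnaire) according to the score at the hearing questionnaire". Section 10 gives the whole primary analysis in one sentence: the two scores are plotted against each other, and "the Pearson correlation coefficient will be calculated". Neither section mentions a confidence interval, a significance test, an alpha level, a smallest correlation of interest or a rank-based alternative.

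The bivariate analyses and logistic regression in Section 10 concern factors related to word deficiency, which is the secondary objective (Section 2.2). The variables listed in Section 3.2 include hearing aid use but not the hearing questionnaire score, so these analyses do not clearly supply inference for the primary relationship.

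Section 8 bases the sample size on recruitment: "Expected new entries are of 10 patients per month", "The recruitment potential is 50 patients over the duration of the study", and, after allowing for refusals and logistics, "we plan to enroll 45 patients". Section 7.3 adds that patients with incomplete evaluations are not replaced.

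Section 4 describes a single-centre case series. Section 12 begins its next step with "If this study does show a link between presbycusis and lexical disorders" and says that a larger multicentre study would then be needed for confirmation.

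**The concern.** Section 12 frames a yes/no outcome, and Section 10 gives no rule for reaching it. Read literally, the plan yields a single number. With 45 patients a coefficient of 0.2 to 0.3 is close to what chance alone can produce, so one author could call it a link and another could call it none. At stake is whether a larger study is launched, or dropped, on a figure whose uncertainty was never displayed.

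A second worry is the choice of Pearson. Naming tests and questionnaires usually have a bounded range. If naming scores gather at the top and hearing complaints at the bottom, a few extreme patients may drive a Pearson coefficient, and a monotone relation may not be linear. A rank correlation would then look like the safer primary measure.

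**Working it through.** **Inputs.** Accrual of 10 patients a month, recruitment potential of 50 and planned enrolment of 45 (Section 8); inclusion period of 5 months (Section 9). The plan states no alpha, so a two-sided 5% level with 95% intervals is assumed throughout.

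**The plan's own figure.** 10 × 5 = 50, which reproduces the recruitment potential; 45/50 = 0.90. The 45 is a feasibility allowance, so there is no statistical target to reproduce or to miss.

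**Precision at n = 45.** Fisher's transformation gives the interval tanh(atanh(r) ± 1.96/√(n − 3)). Here 1/√42 = 0.1543 and 1.96 × 0.1543 = 0.302.

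| Observed r | 95% interval | Half-width |
|---|---|---|
| 0 | −0.29 to 0.29 | 0.29 |
| 0.20 | −0.10 to 0.47 | 0.28 |
| 0.29 | −0.004 to 0.54 | 0.27 |
| 0.30 | 0.01 to 0.55 | 0.27 |
| 0.40 | 0.12 to 0.62 | 0.25 |
| 0.50 | 0.24 to 0.69 | 0.22 |

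The smallest significant |r| is 2.017/√(43 + 2.017²) = 0.294. An interval that includes zero can therefore reach up to about 0.54.

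**Power at n = 45.** Φ(atanh(ρ) × √42 − 1.96) gives 26% at ρ = 0.2, 52% at 0.3, 78% at 0.4 and 95% at 0.5. The correlation detectable with 80% power is tanh(2.80 × 0.1543) = 0.41.

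**Fewer complete patients.** The plan gives no rate of incomplete evaluations. Taking 40 completers as an illustration, 1/√37 = 0.1644. The half-width near zero becomes tanh(0.322) = 0.31, and r = 0.30 has the interval −0.01 to 0.56.

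Every figure in the table needs only r and n, both of which the study will report.

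**Pearson against Spearman.** The documents give neither the range nor the distribution of either score, so the shapes below are assumptions. Power by simulation (4,000 replicates, n = 45, underlying correlation 0.40 in absolute value):

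| Assumed scores | Pearson | Spearman |
|---|---|---|
| Both normal | 79% | 74% |
| About 31% at hearing floor, 20% at naming ceiling | 72% | 72% |
| About 31% at hearing floor, 40% at naming ceiling | 66% | 66% |
| About 50% at hearing floor, 20% at naming ceiling | 64% | 64% |
| Unbounded lognormal hearing score, 20% at naming ceiling, negative correlation | 62% | 73% |
| The same, positive correlation | 56% | 72% |

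The three floor-and-ceiling rows assume a negative correlation, meaning more hearing complaints go with poorer naming. Boundedness alone does not separate the two coefficients. The gap appears only with a heavy, unbounded tail, which is an unlikely shape for a questionnaire score.

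**The case for a change.** The best argument for a change is that an interval can be computed afterwards, but what the sponsor would have called a link cannot be recovered afterwards. A pilot meant to justify a bigger study is also where an interval matters most, because the next study must be sized from the plausible range of the correlation. A few sentences would settle it, with no added patients or visits.

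Part of this stands. No criterion is fixed in advance, and observed values between 0.2 and 0.3 are where that absence could matter: at 45 patients r = 0.30 just excludes zero, and at 40 it does not. Stating the 95% interval and adding a rank correlation as a sensitivity analysis would be harmless good practice.

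It does not make the plan wrong, however. Nothing in Section 10 says that any non-zero coefficient counts as a link, so no stated rule leads to a false conclusion. A binding rule that the interval must exclude zero would turn an exploratory estimate into a significance verdict, which is a matter of style in a single-centre case series. The scatter plot already planned is the usual way to see curvature, ceilings and influential patients, and an analyst who sees them will add a rank coefficient.

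**Conclusion.** No change is required. The missing interval and test are a gap in detail that analysts fill as a matter of course, from two numbers the study will report anyway. The imprecision is real: about ±0.29 near zero and ±0.22 at 0.5 with 45 complete patients, wider with fewer. It follows from a sample size openly set by feasibility, and Section 8 makes no power or precision claim that it contradicts. A mistaken reading of a weak coefficient would lead to a confirmatory study, as Section 12 says, and not directly to a change in care.

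The choice of coefficient is a fair trade-off. Moving to Spearman loses about 5 points of power under normality, is neutral with floors and ceilings, and gains roughly 11 to 16 points (73 − 62 and 72 − 56) only under strong skew.

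These conclusions assume a two-sided 5% level and the score shapes listed above, since the documents give neither. The judgement would differ if the plan had claimed a stated power, or had set a threshold for a link that 45 patients could not support.

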### **7.3. Rules for stopping a person from participating in the research**

At any time, if desired, the patient may withdraw from the study. He will continue to receive the best possible medical care.

Discontinuations from research will be patients for whom evaluations have not been completed. These patients will not be replaced.

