### **11.2. Source data**

All information contained in original documents, or in authenticated copies of these documents, relating to clinical examinations, observations or other activities conducted as part of a research study and necessary for the reconstitution and evaluation of the research. The documents in which the source data are saved are called the source documents.

The data that will be entered directly into the case report form and that will not have any source data as a result are all the scores and reaction times obtained in the lack of word and hearing questionnaires.

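### Section 10 analyses the lack of word score as a number for the main objective but by logistic regression for the secondary one, with no cut-off or limit on factors; linear regression of the score is a cheap improvement

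*Combined protocol and SAP*

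**What the plan says.** Section 3.1 defines the primary outcome as a score: "The lack of word score (BIMM questionnaire) according to the score at the hearing questionnaire". Section 10 treats it as a number for the main objective: "The correlation study between the overall score obtained at the lack of word questionnaire and the score obtained at the hearing questionnaire" is shown as a scatter plot and summarised by Pearson's coefficient. Section 11.2 confirms that the raw values will be available, since the data entered directly in the case report form "are all the scores and reaction times obtained in the lack of word and hearing questionnaires".

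The secondary objective (Section 2.2) concerns variables associated with word loss. Section 3.2 lists them: "Age, gender, socio-cultural level, accommodation, laterality, main diagnosis, hearing aid, speech language therapy according to lack of word score". That is eight candidates, again set against the score. Section 10 says that the study of factors and word deficiency "will be carried out by bivariate analysis and then by logistic regression".

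On size, Section 8 says "we plan to enroll 45 patients". Section 7.3 says of patients with incomplete evaluations: "These patients will not be replaced".

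No section defines word deficiency as a class or as ordered categories. Nor does any section give a cut-off, say how factors are selected or how many may be fitted, or say whether the hearing score enters the model.

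**The concern.** Binary logistic regression needs a yes/no outcome, and the plan describes only a score. Someone must therefore choose a cut. If that happens after the data are seen, the choice could change which factors appear associated. Any cut also discards information that the study has already collected.

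The sample makes this worse. Several listed factors look categorical (gender, laterality and hearing aid, for example). With few patients in the smaller outcome class, an uncommon two-level factor may have an empty cell, so that its odds ratio cannot be estimated. An ordinal logistic model would need no single cut, but the plan does not say that one is meant.

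**Working it through.** **The plan's own figure.** Sections 8 and 9 give 10 patients per month for 5 months: 10 × 5 = 50, which matches the stated recruitment potential. The step to 45 (45/50 = 0.90) has no stated rate. There is no alpha, power or effect size, so there is no power figure to reproduce.

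**Events per candidate factor.** Inputs are 45 patients (Section 8) and eight factors (Section 3.2), each counted as one parameter.
- Best case, median split: the smaller class is at most 22, so 22/8 = 2.75, or 22/9 = 2.4 if the hearing score is a ninth candidate.
- Assumed 70/30 split: 13/8 = 1.6.
- Assumed 80/20 split: 9/8 = 1.1.

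A factor with several levels, or any incomplete patient, lowers these figures.

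**Information kept by a cut.** For a normal score cut at quantile p, the fraction kept is φ(z_p)² / [p(1 − p)].
- p = 0.5: 0.637; × 45 = 28.6 patients.
- p = 0.7: 0.576; × 45 = 25.9.
- p = 0.8: 0.490; × 45 = 22.0.

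**Simulated power.** The settings are n = 45, two-sided 5%, one tested factor with correlation 0.4 with the score, and 3 or 7 independent binary factors without effect. The correlation, splits, prevalences and normal shape are assumptions; the documents give none of them. Monte Carlo error is at most about 1.2 points.

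Continuous tested factor, 5,000 runs, power in %. Ranges cover prevalences of 50, 30 and 15% for the other factors. The last column gives the share of fits with at least one inestimable odds ratio, at those prevalences in that order.

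| Factors | Split | Ordinary linear | HC3 linear | Logistic (Wald) | Any odds ratio not estimable |
|---|---|---|---|---|---|
| 4 | median | 75.2-76.3 | 69.4-70.6 | 52.2-54.3 | 0.0 / 0.2 / 14.8 |
| 4 | 80/20 | 75.1-75.7 | 69.8-70.7 | 39.2-41.4 | 1.3 / 11.3 / 54.1 |
| 8 | median | 71.5-72.5 | 61.7-62.6 | 52.7-54.0 | 0.1 / 0.5 / 32.8 |
| 8 | 80/20 | 71.7-73.2 | 62.2-63.4 | 34.9-37.3 | 4.7 / 26.7 / 85.1 |

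False-positive rates with no effect were 4.6-5.6% (ordinary linear), 3.3-4.9% (HC3) and 4.1-6.6% (Wald).

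Two-level tested factor, four factors fitted, the others at 30% prevalence. The Wald test is poor near separation, so logistic power here is from a Firth-penalised fit (2,000 runs; the other columns 4,000). The last column is for unpenalised logistic regression. Each cell gives median split / 80/20, in %.

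| Prevalence and direction | HC3 linear | Firth logistic | Own odds ratio not estimable |
|---|---|---|---|
| 50% | 74.2 / 73.0 | 59.0 / 44.0 | 0.1 / 10.3 |
| 30%, raises score | 73.4 / 71.2 | 56.5 / 28.1 | 3.2 / 44.8 |
| 30%, lowers score | 72.1 / 73.9 | 56.0 / 51.2 | 3.0 / 2.3 |
| 15%, raises score | 68.7 / 68.7 | 48.9 / 3.4 | 38.3 / 82.7 |
| 15%, lowers score | 67.8 / 68.6 | 49.6 / 56.7 | 34.1 / 9.9 |

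**Skewed score.** With a strongly skewed score (−exp(−0.7s), s normal), four factors and a median split, HC3 linear gives 46-74% against 59-63% for the logistic likelihood-ratio test, whose false-positive rate is 6.3-7.7%. A proportional-odds model of the uncut score is unchanged by skew: power 77.5-79.4%, false-positive rate 6.2-7.6% (four factors, 1,500 runs).

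**The case against.** The strongest reply is that linear regression is not clearly the better model, because nothing in the documents shows the shape of the score. Under the skew tested, HC3 linear had less power than the likelihood-ratio test in three of six settings (59.2 against 60.6, 57.0 against 62.6, 46.1 against 58.9). This stands as a limit on the gain, although the likelihood-ratio test owes part of its advantage to a raised false-positive rate.

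Second, the Wald test flatters the comparison. For a normal score, a continuous factor and a median split, the likelihood-ratio test reaches about 60%, against 70% for HC3 with four factors and 61% with eight. Its false-positive rate there is 6.7% and 8.9%, so the narrower gap is partly bought with error. At 80/20 linear regression stays ahead: 70% against 47% with four factors, 62% against 50% with eight.

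Third, the most extreme figures need 15% prevalence, an 80/20 split or both. With the other factors at 30-50% prevalence and a continuous tested factor, at least one odds ratio is inestimable in under 1% of fits at a median split. That is fair.

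Fourth, the BIMM may have a threshold of its own. The documents do not show one; if it exists, citing it in advance would answer the cut-off point.

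Finally, this is a secondary objective in what Section 4 calls "Monocentric study on a series of cases", and Section 12 foresees a larger confirmatory study. That limits the weight. It does not supply the missing outcome definition or factor limit, which are needed whatever the score's shape.

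**Conclusion.** The concern holds. Section 10 names a method for the secondary objective that, on its usual reading, cannot be run without a cut-off the plan does not give, and it sets no limit on factors for 45 patients. At best there are 2.75 events per candidate factor, a figure that rests on the documents alone. For a roughly normal score, a cut is equivalent to losing about 16 of 45 patients at the median (45 − 29) and 23 at 80/20 (45 − 22). The power differences rest on the assumed correlation of 0.4 and on the assumed splits, prevalences and score shape; under strong skew the advantage of linear regression may vanish. The primary Pearson analysis is untouched. This is worth fixing because it is cheap, but it is not a fatal flaw.

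**What to change.** In Section 10, replace the logistic regression step with:

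> and then by multiple linear regression of the overall lack of word score, including the hearing questionnaire score and a small number of factors from Section 3.2 chosen before the data are analysed (about four model parameters in total), with heteroscedasticity-robust (HC3) standard errors. The remaining factors will be reported bivariately with 95% confidence intervals.

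The sponsor should name the chosen factors and their coding in that sentence; otherwise the selection stays open. Four parameters is a suggestion, not a figure from the documents: 45/4 = 11.25 patients per parameter, against 45/8 = 5.6 if eight are fitted. Linear regression does not by itself cure overfitting, so the limit is needed too.

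Two alternatives also settle the point. If logistic regression is kept, state the cut-off and its source in advance, limit the factors in the same way and use a Firth-penalised fit. If a strongly skewed score is expected, name in advance a proportional-odds model of the uncut score.

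The cost is one sentence, with no extra patients or data. Results become score differences instead of odds ratios. With the hearing score in the model, only about three parameters remain for the listed factors, and one with several levels uses more than one of them, so not all factors are mutually adjusted. HC3 costs about 4-7 points of power with four factors if the residual variance is in fact constant.
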